Tumor samples and blood will be collected at protocol-specified time points. Target expression by immunohistochemistry (IHC) and RNA will be performed retrospectively and there will be no subject preselection. Biomarker assessments from tumor tissue may include protein expression, gene expression, disease subtype classification, tumor microenvironment, and mutational profile. Assessments in blood samples may include cytokine measurements, immunoassays, and circulating nucleic acids. Methods of analysis may include IHC, polymerase chain reaction (PCR), next-generation sequencing, multiplex immunofluorescence, flow cytometry, immunoassays, and proteomic methodologies such as enzyme-linked immunosorbent assay (ELISA) and microvesicle assessment.

Safety Assessments

Safety assessments will include the surveillance and recording of AEs, physical examination findings, vital signs, concomitant medications, pregnancy testing, and laboratory tests. An ongoing, real-time review of subject safety and serious adverse events (SAEs) will be conducted by the sponsor's Drug Safety Department. Adverse event (AE) severity will be graded using the National Cancer Institute Common Terminology Criteria for Adverse Events (NCI CTCAE), version 5.

Statistical Methods

The primary analysis of the study will be performed separately for each cohort in Parts A, B, and C when all treated subjects in the cohort have been followed for at least 6 months or come off study, whichever comes first. The primary efficacy endpoint of confirmed ORR per RECIST v1.1 will be estimated for each cohort based on the full analysis set (FAS), comprising all subjects who received any amount of study treatment. The point estimate of ORR and 90% exact confidence intervals (CIs) using the Clopper-Pearson method will be provided for each cohort.

For the prostate cancer cohort, the confirmed PSA response rate and 90% exact CI will also be presented. The confirmed PSA response is defined as a reduction from baseline PSA level of at least 50%, measured twice ≥ 3 weeks apart.

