3.2.8. Blinding and Unblinding

This is an open-label study.

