4. STUDY POPULATION

Subjects must meet all enrollment criteria to be eligible for this study. Eligibility criteria may not be waived by the investigator and are subject to review in the event of a good clinical practice audit and/or health regulatory authority inspection.

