- Cohort 6, gastric and GEJ adenocarcinoma (Part A and Part B):
 - Must have pathologically-documented gastric or GEJ adenocarcinoma;
 - Must have unresectable locally advanced or metastatic disease;
 - Must have received prior platinum-based therapy;
 - Must have disease progression during or following systemic therapy;
 - Subjects with known human epidermal growth factor receptor 2 (HER2) overexpression must have received prior HER2-targeted therapy;
 - No more than 1 line of prior cytotoxic chemotherapy for their advanced disease;
 - Subjects may have received prior anti-PD(L)1 therapy, unless contraindicated.
- Cohort 7, CRPC (Part B only):
 - Must have histologically or cytologically confirmed adenocarcinoma of the prostate:
 - Subjects with components of small cell or neuroendocrine histology are excluded.
 - Must have metastatic castration-resistant disease:
 - Castration-resistant is defined as progressive disease following adequate medical or surgical (bilateral orchiectomy) castration and testosterone <50 ng/dL (<2.0 nM).
 - Must have been ≥28 days between cessation of androgen receptor-targeted therapy and start of study treatment;
 - Must have received no more than 1 prior line of 2nd generation androgen receptor-targeted therapy (eg, abiraterone acetate, enzalutamide, apalutamide,

- or darolutamide) for metastatic castration-sensitive prostate cancer (CSPC) or CRPC;
- No prior cytotoxic chemotherapy in the metastatic CRPC setting:
 - For subjects who received cytotoxic chemotherapy for CSPC, at least 6 months must have elapsed between last dose of chemotherapy and start of study treatment;
 - No more than 1 prior line of cytotoxic chemotherapy for CSPC
- Subjects with measurable and non-measurable disease are eligible if the following criteria are met:
 - A minimum starting PSA level ≥ 1.0 ng/mL;
 - Subjects with measurable soft tissue disease must have evidence of measurable soft tissue disease according to PCWG3 criteria. Previously normal (<1.0 cm) lymph nodes must have grown by ≥ 5 mm in the short axis to be considered to have progressed;
 - Subjects with nonmeasurable- disease (enrollment after interim analysis and no more than 15 subjects in total) must have documented rising PSA levels or appearance of new lesion according to PCWG3 ([Appendix L](#)):

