 - PSA progression as defined by 2 increases in PSA level over a previous reference value (a minimum of 3 PSA values total) with an interval of ≥ 1 week between each assessment where the PSA value at screening should be ≥ 1 ng/mL, OR
 - Bone disease progression defined by 2 or more new lesions on bone scan
 - Subjects with known breast cancer gene (BRCA) mutations are excluded;
 - No prior radioisotope therapy or radiotherapy to $\geq 30\%$ of bone marrow.
- Cohort 8, melanoma (Part B and Part C):
 - Must have histologically or cytologically confirmed cutaneous malignant melanoma;
 - Subjects with mucosal, acral, or uveal melanoma are excluded.
 - Must have locally advanced unresectable or metastatic stage disease;
 - Must have measurable disease:
 - Lesions that have had prior intralesional therapies including talimogene laherparepvec (T-VEC) are not considered measurable;
 - Subjects with metastases limited to the skin (skin-only metastasis) are excluded.
 - Must have progressive disease following anti-PD(L)1 therapy;
 - No prior cytotoxic chemotherapy in the advanced disease setting;

- No more than 2 prior systemic therapies for advanced disease:
 - Adjuvant therapy within 6 months of diagnosis of advanced disease is considered as 1 line of therapy.
 - Prior anti-CTLA4 therapy is allowed;
 - Prior BRAF +/- mitogen-activated protein kinase (MEK) inhibitor therapy:
 - Part B subjects: May have received BRAF +/- MEK inhibitor therapy if BRAF mutated;
 - Part C subjects: Must have received BRAF +/- MEK inhibitor therapy if BRAF mutated

Inclusion criteria for Parts A, B, and C:

1. Measurable disease according to RECIST v1.1 ([Appendix H](#)) as assessed by the investigator
 - A minimum of one non-nodal lesion ≥ 10 mm in the longest diameter from a non-irradiated area
Or
 - Lymph node lesion ≥ 15 mm in the shortest diameter from a non-irradiated area
 - If target lesion(s) are located within previously irradiated area only, the subject can be enrolled only if there has been demonstrated progression in the “in field” lesion and upon approval of the sponsor’s medical monitor.
2. Age of at least 18 years, or legal age according to local regulations, whichever is older.
3. An Eastern Cooperative Oncology Group (ECOG) Performance Status score of 0 or 1 (see [Appendix J](#) for conversion of performance status using Karnofsky and Lansky scales, if applicable)
4. The following baseline laboratory data:

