6.7. Follow-up

All subjects will be followed for survival until death or study closure, whichever occurs first. Survival and subsequent anticancer therapy follow-up may be conducted with clinic visits or telephone calls.

For subjects who discontinue study treatment for reasons other than progression, the following assessments will be conducted every 6 weeks (± 3 days) for 12 months after the first dose of LV and every 12 weeks (± 7 days) thereafter, until disease progression, initiation of a new anticancer therapy, investigator decision, consent withdrawal, study termination by the sponsor, pregnancy, or death, whichever comes first:

- Physical examination (see Section [7.6.4](#))
- Pregnancy test for subjects of childbearing potential 24 weeks after the last dose of LV (see Section [7.6.5](#))
- CT/MRI scan (see Section [7.2](#) for details); after a year of follow-up, reduce frequency to institution's standard of care
- In subjects who discontinue study treatment due to pregnancy, response assessments should be conducted as appropriate

For prostate cancer subjects who discontinue study treatment for reasons other than progression, the following assessments will be conducted until disease progression, initiation of a new anticancer therapy, investigator decision, consent withdrawal, study termination by the sponsor, or death, whichever comes first:

- Physical examination every 12 weeks (± 7 days) (see Section [7.6.4](#))
- PSA assessment every 12 weeks (± 7 days)
- Bone scan every 12 weeks (± 7 days) (see Section [7.2.1](#))
- Soft tissue tumor assessment (CT/MRI) every 12 weeks (± 7 days) until disease progression for subjects with measurable disease

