9. DATA ANALYSIS METHODS

9.1. Determination of Sample Size

Up to approximately 414 subjects may be enrolled in the study, including up to 72 subjects in Part A (q3wk dosing) with each cohort having up to 12 subjects, up to 252 subjects in Part B (q1wk dosing) with each cohort having up to 30 subjects, and approximately 90 subjects in Part C (monotherapy or combination with pembrolizumab) with each arm having 30 subjects.

Additional cohorts may also be added in future protocol amendments for additional indications, alternative dosing schedule, biopsy/biomarker analysis, and LV based combination therapy.

The sample size is not based on power calculations for a formal hypothesis testing but is selected to provide a degree of characterization of commonly occurring AEs in the safety profile and/or a reasonable estimation precision of ORR.

For a sample size of 30 subjects per cohort/arm, assuming confirmed ORR is between 10% and 50%, and confirmed PSA response rate for CRPC is between 10% and 50%, the 2-sided 90% exact confidence interval (CI) are summarized below:

Confirmed ORR*	90% Exact CI (N=30)
10%	(3%, 24%)
20%	(9%, 36%)
30%	(17%, 47%)
40%	(25%, 57%)
50%	(34%, 66%)

*Including confirmed PSA response rate for CRPC cohort

This sample size of 30 subjects per cohort/arm would additionally provide the following probabilities of observing at least 1 patient having an AE, as summarized below.

True AE Incidence Rate	Probability of Observing at Least One Patient Having an AE (N=30)
5%	79%
10%	96%

In Part B, the initial 12 subjects enrolled across the tumor cohorts per dose level will be evaluated for safety after the 12th patient completes the first cycle of treatment. The sample size of 12 allows for a reasonable likelihood of observing a given AE in at least 1 subject even when the incidence of the specific AE is low.

The table below shows the probability of observing an AE in at least 1 subject out of 12 subjects for different underlying incidence of AEs.

Underlying AE Incidence	Probability of Observing the AE in 1 or More Subjects Out of 12 Subjects
1%	11%
5%	46%
10%	72%

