9.2. Study Endpoint Definitions

9.2.1. Confirmed ORR

Confirmed ORR is defined as the proportion of subjects who achieve a confirmed CR or PR according to RECIST v1.1 as assessed by the investigator. Subjects who do not have at least 2 post-baseline response assessments (initial response and confirmation scan) will be counted as non-responders.

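### Cohort 7 (CRPC): Section 4.1 both admits and excludes non-measurable disease; if such subjects enrol, the all-treated RECIST ORR depends on their number and the CRPC column of Table 20 no longer matches it

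*Protocol*

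**What the plan says.** **Eligibility.** In Protocol Section 4.1, the Cohort 7 criteria admit measurable and non-measurable disease, the latter as: "Subjects with nonmeasurable- disease (enrollment after interim analysis and no more than 15 subjects in total"). Later in the same section, item 1 of the criteria common to Parts A, B and C is "Measurable disease according to RECIST v1.1", with no exception for Cohort 7. Section 4 adds: "Subjects must meet all enrollment criteria to be eligible for this study". Section 6.7 asks for soft-tissue imaging of prostate subjects in follow-up "until disease progression for subjects with measurable disease", which expects some subjects without it.

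**Endpoint and denominator.** Section 9.2.1: "Confirmed ORR is defined as the proportion of subjects who achieve a confirmed CR or PR according to RECIST v1.1". Section 9.3.5.1 makes this primary for every tumor type and adds confirmed PSA response as another primary endpoint for prostate cancer. The Synopsis says that ORR "will be estimated for each cohort based on the full analysis set (FAS), comprising all subjects who received any amount of study treatment". Section 9.3.1.7 has no measurable-disease set, and its efficacy evaluable set does not require measurable disease. PSA response has its own evaluable set (Section 9.3.5).

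**Response criteria.** Appendix H defines PR as shrinkage of target lesions and CR as their disappearance. It is an extract; Appendix I shows that RECIST v1.1 also covers non-target disease.

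**Interim.** Section 9.3.9 projects each cohort to 30 subjects. Success for CRPC is a posterior probability above 90% that ORR exceeds 30%. Table 20 prints predictive probabilities of success (PPoS) of 6%, 21% and 48% for 3, 4 and 5 responses in 12.

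**SAP.** It is written to the original protocol and covers Cohorts 1 to 6 only.

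**The concern.** A site cannot apply both eligibility statements. The statistical consequence depends on which one governs.

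If non-measurable subjects are treated, they count in the denominator of a primary endpoint for which they cannot have a PR. The CRPC ORR, read against a 30% standard-of-care rate, would then move with post-interim case mix even if the drug's activity were constant.

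The interim projection has the matching problem. The first 12 subjects all have measurable disease, but up to 15 of the next 18 need not, and Table 20 treats all 18 as equally able to respond.

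**Working it through.** Let k be the number of non-measurable subjects among 30. The plan caps k at 15 and gives no expected value.

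**1. Dilution of ORR.** If non-measurable subjects have no CR, all-treated ORR = measurable-disease ORR × (30−k)/30. For a true 40%:

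- k=3: 0.40 × 27/30 = 36%
- k=5: 0.40 × 25/30 = 33%
- k=10: 0.40 × 20/30 = 27%
- k=15: 0.40 × 15/30 = 20%

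If 5% to 10% of non-measurable subjects had a CR (an assumption), add k × rate / 30. The results become 34% to 35% (k=5), 28% to 30% (k=10) and 23% to 25% (k=15). At the cap, 6 responders give a Clopper-Pearson 90% CI of 9% to 36% as 6/30, or 19% to 64% as 6/15.

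**2. Reproducing Table 20.** Inputs from Section 9.3.9: 12 subjects at interim, 30 in total, p0 = 30%, posterior threshold 90%. The prior is not stated. Beta(p0+0.075, 0.925−p0) reproduces every printed cell of the 10%, 15% and 30% columns after rounding, so it is used here as an inferred prior; for CRPC it is Beta(0.375, 0.625).

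- Success cut-off: posterior P(ORR>30%) is 0.873 at 12/30 and 0.935 at 13/30, so 13 responses are needed.
- PPoS(x) = P(BetaBinomial(18, 0.375+x, 0.625+12−x) ≥ 13−x).
- For x = 0 to 5: 0.0007%, 0.05%, 0.8%, 5.6%, 20.9%, 47.9%. Printed: 0.0007%, 0.05%, 0.8%, 6%, 21%, 48%.

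The cut-off is also 13/30 under the other five priors tried: uniform, Jeffreys, Beta(0.3,0.7), Beta(0.35,0.65) and Beta(0.4,0.6).

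**3. PPoS for the all-treated endpoint.** Keep the cut-off at 13/30 and replace 18 by 18−k future subjects able to respond (no non-target CR):

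| Interim | Printed | k=3 | k=4 | k=5 | k=10 |
|---|---|---|---|---|---|
| 4/12 | 21% | 10.3% | 7.3% | 4.8% | 0% |
| 5/12 | 48% | 31% | – | 20% | 0.6% |

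Across the six priors, 4/12 gives 9.7% to 12.2% at k=3, 6.9% to 8.7% at k=4 and 4.5% to 5.8% at k=5. Adding Binomial(k, 10%) complete responders under the inferred prior gives 10.1% at k=4. The crossing below 10% at 4/12 therefore falls at k=3 to 5, depending on the prior and the CR rate. At 3/12 PPoS is already 5.6% at k=0; with no non-target CR it is lower for every k above 0.

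**4. PPoS with a measurable-disease denominator.** Let N be the final number with measurable disease. Recompute the cut-off for N and project N−12 subjects (inferred prior):

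| N | Cut-off | PPoS at 4/12 | PPoS at 5/12 |
|---|---|---|---|
| 27 | 12 | 17.8% | 44.5% |
| 25 | 11 | 18.5% | 46.7% |
| 20 | 9 | 14.4% | 44.3% |
| 18 | 9 | 4.2% | 24.0% |
| 15 | 7 | 5.5% | 38.0% |

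For N of 15 to 19 and 21, PPoS at 4/12 lies between 2.5% and 9.4%, so the under-10% region becomes 4 or fewer of 12.

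**The case against.** The strongest reply is that the two halves of the point are alternatives. If the common criterion governs, k=0, ORR is not diluted and Table 20 stands. That is correct, and the dilution is claimed only for the other reading, which Section 6.7 supports but does not settle.

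It can also be said that non-measurable subjects have a primary endpoint of their own in PSA response, that an all-treated ORR is a valid and conservative estimate in a descriptive cohort, and that a later SAP may add a measurable-disease analysis. All of this stands. It is why the all-treated ORR should still be reported. But RECIST ORR remains primary for CRPC, and no current passage names a measurable-disease analysis.

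The 30% benchmark is a further difficulty. Section 9.3.9 attributes it to Section 3.1, which does not give it, so the documents do not show whether it describes measurable disease or all CRPC.

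A reader might infer more than the documents support:

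- *That the CRPC ORR will be halved.* Fifteen is a cap, and no k is planned.
- *That the futility rule is wrong.* Non-measurable subjects enter only after the interim, so the first-12 count is untouched. The printed stop at 3 or fewer of 12 is non-binding, and no formal test is planned at 30.
- *That these subjects cannot respond at all.* Appendix H gives them no PR route, but a CR on non-target disease is not ruled out.
- *That 4/12 always falls below 10% from k=4.* With a 10% CR rate it is 10.1%.

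**Conclusion.** The eligibility contradiction is in the current text and needs correcting whatever view is taken of the statistics. The dilution of ORR is conditional on the Cohort 7 text governing and grows with an unstated k: none at k=0, and 40% shown as 33% at k=5 or 20% at the cap, assuming no non-target CR.

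The mismatch with Table 20 is secondary. It makes the printed 21% and 48% too high for the all-treated endpoint once k exceeds 0, and it rests on an inferred prior, though the six priors tried agree closely. PSA response is not affected. This should be fixed, but it does not invalidate the interim rule.

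**What to change.** Reconcile the Cohort 7 criteria with common inclusion criterion 1. If non-measurable CRPC subjects remain eligible:

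- **(a)** Define CRPC RECIST ORR among treated subjects with measurable disease at baseline, and report the all-treated ORR beside it.
- **(b)** State that the CRPC column of Table 20 assumes 30 measurable subjects, or recompute it for the planned measurable N. Item (a) alone brings PPoS close to the printed values at N=25 or 27, and less closely at N=20. It does not do so at N of 15 to 19 or 21, so recompute if the planned N is that small.
- **(c)** Restate ORR precision for that N. At 40% the 90% CI is 25%–57% (N=30), 24%–58% (N=25), 22%–61% (N=20) or 19%–64% (N=15).
- **(d)** Say whether a CR on non-target disease counts as a response, and whether the 30% benchmark refers to measurable disease.

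Specify this before any non-measurable subject's data are analysed, because "This is an open-label study". Leave PSA response on its own evaluable set.

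The cost is a protocol clarification and SAP text. The ORR interval widens slightly at N=25 and more at N=15. No extra patients are needed unless the sponsor wants 30 with measurable disease.

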4.2. Exclusion Criteria

Parts A, B, and C

1. Subjects with active concurrent malignancy or a previous malignancy within the past 3 years are excluded. Exceptions are malignancies with a negligible risk of metastasis or death (eg, 5-year OS $\geq 90\%$), such as adequately treated carcinoma in situ of the cervix, non-melanoma skin carcinoma, localized prostate cancer, ductal carcinoma in situ, or Stage I uterine cancer, and does not interfere with the evaluation of the study therapy efficacy or safety.
2. Any anticancer therapy (such as cytotoxic chemotherapy, biologic therapy, immunotherapy etc.) within 3 weeks of starting study treatment. Subjects who are/were on adjuvant hormonal therapy for the treatment of malignancies with negligible risk of metastases (as described in exclusion criteria 1) are eligible.
3. Subjects with known active central nervous system (CNS) lesions (including leptomeningeal metastasis) are excluded. Subjects with symptoms concerning for active CNS disease must have been evaluated and treated per institutional standard of care. Subjects with definitively treated brain metastasis (surgery and/or radiotherapy) are eligible if they meet the following criteria:
 - Asymptomatic from the CNS metastases
 - Completely off steroids; anti-convulsants at a stable dose are allowed.
 - No evidence of clinical and radiographic disease progression in the CNS for ≥ 3 weeks after definitive radiotherapy and/or surgery
4. Active viral, bacterial, or fungal infection requiring systemic treatment within 7 days prior to the first dose of LV. Routine antimicrobial prophylaxis is permitted.
5. Subjects with any ongoing clinically significant toxicity (Grade 2 or higher, per the NCI CTCAE, v5.0) associated with prior treatment (including systemic therapy, radiotherapy, or surgery) are not permitted (except alopecia).
6. Ongoing sensory or motor neuropathy of Grade ≥ 2
7. Subjects with known and untreated hepatitis B, hepatitis C, or human immunodeficiency virus (HIV). Subjects are eligible if they are on a stable anti-viral treatment or have received curative therapy (check [Appendix F](#) for a list of drug-drug interactions).
 - **Part C Arm 2 and Arm 3 only:**
 - HIV+ subjects with a history of Kaposi sarcoma and/or Multicentric Castleman Disease are not eligible.
 - HIV+ subjects on anti-retroviral therapy (ART) must meet the following criteria to be eligible:
 - CD4+ T-cell count >350 cells/mm³ at time of screening
 - Confirmed HIV RNA level below 50 copies/ml or the lower limit of qualification (below the limit of detection) using the locally available assay at the time of screening and for at least 12 weeks prior to screening

- Stable ART regimen with no changes in drugs or dose modification for at least 4 weeks prior to study entry (Day 1)

8. Current therapy with other systemic antineoplastic or investigational agents
9. Subjects who are breastfeeding, pregnant, or planning to become pregnant from time of informed consent until 6 months after the final LV administration
10. Known hypersensitivity to any excipient contained in the drug formulation of LV (all Parts) or pembrolizumab (Part C only).
11. Documented history of a cerebral vascular event (stroke or transient ischemic attack), unstable angina, myocardial infarction, or cardiac symptoms consistent with congestive heart failure, Class III-IV, by New York Heart Association criteria within 6 months prior to study enrollment ([Appendix E](#)).
12. Has received prior radiotherapy within 2 weeks of start of study treatment. A subject is also excluded if radiotherapy occurred more than 2 weeks prior to start of study treatment but the subject has not recovered from radiation-related toxicities, requires corticosteroids, or has had radiation pneumonitis.
13. Other serious or uncontrolled underlying medical condition that, in the opinion of the investigator, would impair the subject's ability to receive or tolerate the planned treatment and follow-up (eg, active cardiac disease, active systemic infection, chronic conditions, any psychiatric or substance abuse disorders), interfere with the subject's cooperation with the requirements of the trial, place the subject at undue risk of SAE, or make the subject unable to receive sustained therapy
14. Has received a live vaccine within 30 days of the planned start of study therapy. Seasonal influenza vaccines for injection are generally inactivated and are allowed; however, intranasal influenza vaccines (eg, Flu-Mist) are live attenuated vaccines and are not allowed.

Part C Only

15. Has received prior therapy with an anti-PD-1, anti-PD-L1, or anti-PD-L2 agent or with an agent directed to another stimulatory or co-inhibitory T-cell receptor (eg CTLA-4, OX 40, CD137), and was discontinued from that treatment due to a Grade 3 or higher immune-related adverse event (irAE).
16. Active autoimmune disease that has required systemic treatment in past 2 years (i.e., with use of disease modifying agents, corticosteroids, or immunosuppressive drugs). Replacement therapy (eg, thyroxine, insulin, or physiologic corticosteroid replacement therapy for adrenal or pituitary insufficiency) is not considered a form of systemic treatment.
17. Has had an allogenic tissue/solid organ transplant.
18. History of interstitial lung disease.
19. Current pneumonitis, or history of (non-infectious, including radiation induced) pneumonitis that required steroids.

20. Has a diagnosis of immunodeficiency or is receiving chronic systemic steroid therapy (in doses exceeding 10 mg daily of prednisone equivalent) or any other form of immunosuppressive therapy within 7 days prior to the first dose of study treatment. The use of corticosteroids for physiological replacement may be approved after consultation with the sponsor.

